15.0 DATA MANAGEMENT/CONFIDENTIALITY

The investigator will ensure that data collected conform to all established guidelines. Each subject is assigned a unique subject number to protect subject confidentiality. Subjects will not be referred to by this number, by name, or by any other individual identifier in any publication or external presentation. The licensed medical records department, affiliated with the institution where the subject receives medical care, maintains all original inpatient and outpatient chart documents.

Subject research files are stored in a secure place (or database). Access is restricted to authorized personnel.

15.1 Data Quality Assurance

Accurate and reliable data collection will be ensured by verification and crosscheck of the eCRFs against the investigator's records by the study monitor (source document verification) and by the maintenance of a drug-dispensing log by the investigator.

15.2 Data Documents

The investigator must ensure that the records and documents pertaining to the conduct of the study and the distribution of the investigational product are complete, accurate, filed, and retained. Examples of source documents include: hospital records; clinic and office charts; laboratory notes; memoranda; checklists; dispensing records; recorded data from automated instruments; copies or transcriptions certified after verification as being accurate copies; microfiche; x-ray film and reports; and records kept at the pharmacy; and the laboratories, as well as copies of CRFs or CD-ROM.

15.3 Data Management

Data will be collected and entered into the eCRF. These data will be electronically verified through use of programmed edit checks specified by the clinical team. Discrepancies in the data will be brought to the attention of the clinical team, and investigational site personnel, if necessary. Resolutions to these issues will be reflected in the database. An audit trail within the system will track all changes made to the data.

15.4 Investigator Responsibilities for Data Collection

The investigator is responsible for complying with the requirements for all assessments and data collection (including subjects not receiving protocol-required therapies) as stipulated in the protocol for each subject in the study. For subjects who withdraw prior to completion of all protocol-required visits and are unable or unwilling to continue the Schedule of Assessments (in Appendix B, the investigator can search publicly available records (where permitted) to ascertain survival status.

This ensures that the data set(s) produced as an outcome of the study is/are as comprehensive as possible.

16.0 STATISTICAL CONSIDERATIONS

16.1 Study Design

The first six subjects (may expand up to 18) treated with avelumab combined with trabectedin will constitute the Phase 1 portion of the trial. If the combination is safe, the trial will be expanded to treat an additional 16 subjects. If a dose reduction is required based on 2 out of 6 subjects in the first phase having DLT, a dose reduction will be made, first to 1.0 mg/m² and if <2 subjects have DLTs at that dose, re-escalated to 1.2 mg/m². An additional 16 Phase 2 subjects will accrue using the highest dose tolerated with <2 DLTs.

A data and safety monitoring board will review any dose limiting toxicities that should arise on the Phase I portion of the trial. The DSMB will also review any DLTs in the extension portion of the trial at meetings described in the DSMB Charter. Should more than 30% of subjects have DLTs, accrual will halt until the DSMB can meet to advise on whether the trial may resume, with or without modification. Subjects on the Phase I portion of the study will also be included in the efficacy analysis.

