Enrollment during the first cohort of the Phase 1 portion of the trial will be staggered. The first subject must have received their second dose of both avelumab and trabectedin prior to treatment of the second subject, and the second subject must have received their second dose of both avelumab and trabectedin prior to treating the third subject. In cases where the first subject's second doses of avelumab and/or trabectedin is delayed beyond week 4, either due to trabectedin toxicity or DLT, or is withdrawn or discontinued from the study, the second subject will be allowed to enroll and start therapy. However, the second subject must complete their second dose of trabectedin and avelumab prior to the start of the third subject.

Should 2 or more DLTs be observed in the first 6 subjects, the starting trabectedin dose will be reduced to 1 mg/m² and the Phase 1 will expand to enroll an additional 6 subjects at the new starting dose. Should two or more DLTs be observed in the 6 subjects enrolled at 1 mg/m² the study will go on hold and a DSMB will meet to discuss if there are modifications that could allow the protocol to safely be re-opened. If <2 DLTs are observed in the 6 subjects on the 1.0 mg/m² cohort, enrollment will expand to a third cohort, enrolling an additional 6 subjects at 1.2 mg/m² of trabectedin. If 2 or more DLTs are observed at 1.2 mg/m², then 1.0mg/m² will be determined to be the recommended Phase 2 dose (RP2D). The highest dose with <2 DLTs will be selected for Phase 2 dosing. If one of the first six subjects does not complete the DLT period for a reason unrelated to toxicity (for example withdrawal of consent or tumor progression) that subject may be replaced.

In Phase 2, the study will go on hold and a DSMB meeting will be triggered if more than 30% of subjects have unexpected, probably related SAE's grade 3 or higher that do not resolve to grade 2 within 2 weeks.

In any subsequent Phase 1 cohorts (1.0 mg/m² dosing and 1.2 mg/m² dosing of trabectedin) subjects may be treated concurrently without delay. Prior to beginning Phase 2, each subject on the phase 1 portion must have received their second dose of both avelumab and trabectedin or completed their treatment (e.g. come off study for symptomatic progression).

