4.2 Estimated Accrual

- **Phase 1:** 6 subjects, may expand up to 18
- **Phase 2:** 16 subjects

A minimum of 22, and up to a possible total of 34 subjects are anticipated to receive treatment.

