16.2 Phase I Design

The primary objective of the Phase I component of this study is to evaluate the safety of avelumab given in combination with trabectedin among subjects with advanced L-type sarcomas. The phase I component of this study will treat 6 subjects (modified 3+3 design) to demonstrate safety of the combination. Dose-limiting toxicities will be defined as unexpected, probably-related toxicities of grade 3 or higher.

The study design is as follows:

6 subjects will be treated initially.

- If 2 or more subjects experience a DLT at any point during the Phase 1 portion, a new cohort will be added, enrolling an additional 6 subjects at a reduced dose of 1 mg/m² trabectedin.
- Should 2 or more of these next 6 subjects at the reduced dose have a DLT, stop and convene DSMB meeting to recommend changes to the protocol.
- If at any time in the study (including those above) 30% of subjects have a DLT, have a DSMB meeting to review specific toxicities. We will re-calculate the percent of subjects who have had a DLT each time there is a new DLT.

If <2 subjects have DLTs on the 1 mg/m² dose level, another Phase I cohort of 6 subjects implemented, re-escalating to 1.2 mg/m² dosing of trabectedin. If <2 DLTs are seen there, that will be the recommended Phase II dose. If 2 or greater DLTs are seen there, the Phase 2 will move forward at the 1.0 mg/m² dose level, after discussion with the DSMB.

Safety analysis will continue through the entire trial, if at any point during the trial 30% of subjects experience a DLT, the trial should halt and convene a meeting of the DSMB.

A total of up to 18 subjects may enroll on Phase 1, and an additional 16 on Phase 2.

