16.3 Phase II Design

The primary objective of the Phase II portion is to compare the objective response rate (ORR) with historical rates for single agent trabectedin. Subjects from the Phase I portion of the trial who are treated at the dose ultimately used in the expansion will be included in the efficacy analysis. Our null hypothesis estimates the overall response rate of single agent trabectedin at 9.9%. We believe an increase in the response rate to 35% would be highly compelling. A total subject number of 22 gives us an 85% power to detect this increased response rate assuming a two-sided alpha of 0.05. 6 or more subjects with responses would suggest clinical activity of this regimen over single agent trabectedin.

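### Sections 16.1 and 16.3 define the Phase I contribution to the primary response analysis differently, so after a de-escalation the set could be 34 or 22 subjects

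*Combined protocol and SAP*

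**What the plan says.** Overall response rate by RECIST 1.1 is a primary endpoint (section 3.1.2). Two sentences say which Phase I subjects enter its analysis.

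- Section 16.1, after describing a reduction to 1.0 mg/m² and re-escalation to 1.2 mg/m²: "Subjects on the Phase I portion of the study will also be included in the efficacy analysis". No dose condition is attached.
- Section 16.3, beside the hypothesis and sample size: "Subjects from the Phase I portion of the trial who are treated at the dose ultimately used in the expansion will be included".

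Section 16.3 sets the null rate at 9.9% and the target at 35%, and continues: "A total subject number of 22 gives us an 85% power to detect this increased response rate assuming a two-sided alpha of 0.05". The decision rule follows as a bare count: "6 or more subjects with responses would suggest clinical activity of this regimen over single agent trabectedin".

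On enrolment, section 16.2 says "A total of up to 18 subjects may enroll on Phase 1, and an additional 16 on Phase 2", and section 4.2 says "A minimum of 22, and up to a possible total of 34 subjects are anticipated to receive treatment".

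Sections 4.1.2 and 16.2 set the cohort rules. Two or more DLTs among the first six subjects add six at 1.0 mg/m². Fewer than two DLTs there add six more at 1.2 mg/m². Phase 2 then runs at 1.2 or 1.0 mg/m², according to the DLTs in the 1.2 mg/m² cohort. If the 1.0 mg/m² cohort has two or more DLTs, the study goes on hold and "a DSMB will meet to discuss if there are modifications that could allow the protocol to safely be re-opened".

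Two further provisions bear on the count. Section 4.1.2 allows a replacement: "If one of the first six subjects does not complete the DLT period for a reason unrelated to toxicity", that subject may be replaced. Sections 4.1.1 and 10.4 let an individual subject's trabectedin dose be reduced during treatment, first to 1.2 and then to 1.0 mg/m².

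**The concern.** Both sentences define membership of the same efficacy analysis, and they agree only if the starting dose is never reduced. After a de-escalation, 16.1 brings in every Phase I cohort and 16.3 brings in one. The plan does not say which takes precedence.

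The denominator of a primary endpoint is therefore not fixed on paths that the protocol itself provides for. The trial is open-label and single-arm, so responses will be visible as they occur. With two written rules available, the set could be chosen after the results are known. Twelve of the 34 subjects would have started at a dose not carried into Phase 2.

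The wording about being treated at a dose in 16.3 is also open. A subject who started higher and was reduced to the expansion dose could be counted or left out.

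**Working it through.** **Inputs.** From 16.3: null rate 0.099, target rate 0.35, n = 22, cut-off 6, two-sided alpha 0.05. From 4.1.2, 16.1 and 16.2: six subjects per Phase I cohort, up to three cohorts, 16 subjects in Phase 2.

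**Step 1. Reproduce the plan's figures.** With X binomial(n, p):

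- Upper-tail error: P(X ≥ 6 | 22, 0.099) = 1 − Σ(k=0..5) C(22,k) 0.099^k 0.901^(22−k) = 0.0174.
- With a cut-off of 5 the upper tail is 0.060, so 6 is the smallest count with an upper tail of at most 0.025.
- Power: P(X ≥ 6 | 22, 0.35) = 0.837, against a stated 85%. This is close enough to treat as reproduced.

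**Step 2. Count the two sets** (six per cohort, no replacement, dose taken as assigned starting dose).

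| Path to Phase 2 | Phase I total | Set under 16.1 | Set under 16.3 |
|---|---|---|---|
| No de-escalation, Phase 2 at 1.5 mg/m² | 6 | 6 + 16 = 22 | 6 + 16 = 22 |
| 1.5, then 1.0, then 1.2; Phase 2 at 1.2 mg/m² | 18 | 18 + 16 = 34 | 6 + 16 = 22 |
| 1.5, then 1.0, then 1.2; Phase 2 at 1.0 mg/m² | 18 | 18 + 16 = 34 | 6 + 16 = 22 |
| Two or more DLTs at 1.0 mg/m², hold | 12 | not defined | not defined |

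The difference is 34 − 22 = 12 subjects, 12/34 = 35% of the larger set. The 34 as an efficacy set is our sum; the plan gives 34 only as maximum accrual.

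**Step 3. What six responses mean in each set.**

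| | 6 of 22 | 6 of 34 |
|---|---|---|
| Observed rate | 27.3% | 17.6% |
| Exact (Clopper-Pearson) 95% CI | 10.7% to 50.2% | 6.8% to 34.5% |
| Upper tail at 9.9% | 0.0174 | 0.114 |
| Two-sided p, doubled tail | 0.0348 | 0.229 |
| Two-sided p, minimum likelihood | 0.0174 | 0.143 |

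Six responses exclude 9.9% at n = 22 but not at n = 34. Keeping the cut-off of 6 at n = 34 would raise the upper-tail error by a factor of 0.1143/0.0174 = 6.6. At n = 34 an upper tail of at most 0.025 needs 8 responses (0.0159; 7 responses give 0.046).

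**Step 4. Sensitivity to the common-rate assumption.** The 0.114 takes 9.9% at every dose level. Suppose instead that the 12 subjects at other starting doses have null rate x (an assumption; the plan gives none). P(Bin(22, 0.099) + Bin(12, x) ≥ 6) is then 0.054 at x = 5%, 0.076 at 7%, 0.147 at 12% and 0.200 at 15%.

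**Step 5. How often the conflict would arise.** Let q1 and q2 be the DLT probabilities per subject at 1.5 and 1.0 mg/m². A written de-escalation path reaches Phase 2 with probability

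[1 − (1−q1)^6 − 6·q1·(1−q1)^5] × [(1−q2)^6 + 6·q2·(1−q2)^5].

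The plan gives no DLT rates, so these are assumptions:

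- Common rate of 10%: 0.101; 20%: 0.226; 25%: 0.249; 30%: 0.244; 40%: 0.179; 50%: 0.097.
- 30% at 1.5 and 10% at 1.0 mg/m²: 0.5798 × 0.8857 = 0.514.

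These products also assume that the DSMB lets the written path continue. Two DLTs in six subjects is 33%, above the 30% trigger for DSMB review.

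**Step 6. One replacement.** If the replaced subject is also counted, n = 23. P(X ≥ 6 | 23, 0.099) = 0.0216, with two-sided p 0.0432 (doubled) or 0.0216 (minimum likelihood). Five of 23 gives 0.141 or 0.071. The cut-off stays at 6.

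**The case against.** The best defence is that the two sections can be read together: 16.1 is an overview saying that Phase I subjects contribute, and 16.3 says which ones. Section 16.3 is where the hypothesis, sample size and cut-off are set. Its n = 22 equals 6 + 16 on every written path to Phase 2 only under the dose-restricted rule. This is probably what was intended, and it shows which wording to keep. It does not remove the conflict, because 16.1 is unqualified, follows a description of the de-escalation, and does not refer to 16.3.

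A second objection is that the 0.114 needs three things at once: a de-escalation, 16.1 read literally, and the cut-off of 6 moved to 34 subjects. That is correct. No text moves the cut-off, which stands directly after the total of 22. The 0.114 is the consequence of a possible misapplication and not an error rate of the design. The choice between 22 and 34 subjects needs only the first two conditions.

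Third, the DLT rates and the alternative null rates are assumptions, and the path probabilities ignore DSMB intervention. That also stands; they show that the trigger is plausible, not how likely it is.

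Fourth, 4.1.2 speaks of starting doses when it defines the later cohorts, so the wording in 16.3 can naturally be read as the cohort dose. That is a fair reading, but 16.3 does not say it.

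**Conclusion.** The concern holds. As written, 16.1 and 16.3 contradict each other on the primary response set. The effect is conditional: with no de-escalation both rules give 22 subjects, and the sample size, power and cut-off stand. After either written de-escalation path to Phase 2 the set is 34 under 16.1 read literally and 22 under 16.3, assuming six subjects per cohort, no replacement, and dose meaning assigned starting dose. If the study is held at 1.0 mg/m² and later re-opened with modifications, neither section defines a number.

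The worst consequence is an upper-tail error of 0.114 in place of 0.0174. It requires the cut-off of 6 to be kept at 34 subjects and a common 9.9% rate; the range is 0.054 to 0.200 if the other starting doses have null rates of 5% to 15%. This should be corrected before response data are analysed.

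**What to change.** - **Section 16.1:** replace the unrestricted sentence with one that matches 16.3. The primary response set is all Phase 2 subjects plus those Phase I subjects whose assigned starting trabectedin dose is the one carried into Phase 2. Responses in other Phase I subjects are described separately.
- **Section 16.3:** use the term assigned starting dose here too, so that later reductions in an individual subject do not change membership of the set.
- **Section 16.3:** state that the cut-off of 6 applies to n = 22. If the actual number differs, for example after a replacement or a re-opening, the conclusion rests on an exact binomial test against 9.9% at the actual n, at the plan's two-sided 0.05. Name the two-sided convention. The choice does not alter the cut-off at n = 22 or 23.

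The cost is one sentence in 16.1 and one or two in 16.3, with no extra patients or procedures and no change to dosing or the DLT rules. The drawback is that Phase I subjects who started at other doses do not count toward the primary test, which is already the effect of 16.3 on the starting-dose reading.

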16.2 Phase I Design

The primary objective of the Phase I component of this study is to evaluate the safety of avelumab given in combination with trabectedin among subjects with advanced L-type sarcomas. The phase I component of this study will treat 6 subjects (modified 3+3 design) to demonstrate safety of the combination. Dose-limiting toxicities will be defined as unexpected, probably-related toxicities of grade 3 or higher.

The study design is as follows:

6 subjects will be treated initially.

- If 2 or more subjects experience a DLT at any point during the Phase 1 portion, a new cohort will be added, enrolling an additional 6 subjects at a reduced dose of 1 mg/m² trabectedin.
- Should 2 or more of these next 6 subjects at the reduced dose have a DLT, stop and convene DSMB meeting to recommend changes to the protocol.
- If at any time in the study (including those above) 30% of subjects have a DLT, have a DSMB meeting to review specific toxicities. We will re-calculate the percent of subjects who have had a DLT each time there is a new DLT.

If <2 subjects have DLTs on the 1 mg/m² dose level, another Phase I cohort of 6 subjects implemented, re-escalating to 1.2 mg/m² dosing of trabectedin. If <2 DLTs are seen there, that will be the recommended Phase II dose. If 2 or greater DLTs are seen there, the Phase 2 will move forward at the 1.0 mg/m² dose level, after discussion with the DSMB.

Safety analysis will continue through the entire trial, if at any point during the trial 30% of subjects experience a DLT, the trial should halt and convene a meeting of the DSMB.

A total of up to 18 subjects may enroll on Phase 1, and an additional 16 on Phase 2.

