4.0 TRIAL OVERVIEW

4.1 Study Design

4.1.1 Introduction

This is a Phase I/II, non-randomized, open-label, interventional study of avelumab combined with trabectedin for subjects with advanced L-type sarcoma.

The Phase I stage will evaluate trabectedin (1.5 mg/m²) combined with avelumab (800 mg flat dose). Dose reduction for the trabectedin therapy is permitted after the first cycle. Events which would require a dose reduction of trabectedin are outlined in Section 10, however additional dose reductions may be made at the discretion of the treating clinician down to a lowest possible dose of 1 mg/m². There will be no dose escalation or re-escalation of trabectedin.

4.1.2 Definition of dose limiting toxicity (DLT):

During the phase I portion of the protocol, a DLT will be defined as any grade 3 or higher adverse events, at least possibly-related to protocol therapy, which occur during the first 6 weeks of treatment, with the following specifications and limitations:

- Lab abnormalities that have no clinical sequelae (e.g. febrile neutropenia from low ANC, bleeding from thrombocytopenias etc.) and resolve to grade 1 or better within 7 days will not be considered a DLT.
- Any elevation in total bilirubin > 2x institutional ULN will be considered a DLT.
- Any elevation in AST and ALT over 8x institutional ULN will be considered a DLT.
- ANC <500/ μ L lasting 5 days or more will be considered a DLT.
- Platelets < 25,000/ μ L (grade 4 toxicity) lasting 5 days or more will be considered a DLT.
- Hemoglobin < 7.0 lasting 5 days or more will be considered a DLT.

Additionally, should any grade 5 toxicity (death) occur that is at least possibly-related to treatment (e.g. not easily otherwise explained; for example: a car accident), this will be considered a DLT. In the event of any grade 5 toxicity, enrollment will immediately be put on hold and a data safety monitoring board (DSMB) meeting will be requested immediately.

All clinically significant grade 3 or higher toxicities will be recorded and presented to the DSMB at scheduled meetings. Expected toxicities are those outlined in [Section 10](#). The DSMB will be specifically instructed to consider whether there are increased frequency of known toxicities and to make recommendations accordingly if appropriate. Section 10 summarizes criteria for required dose adjustments.

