9.6 Attribution of an Adverse Event

Association or relatedness to the study agent will be assessed by the investigator as follows:

- **Definite:** The event follows a reasonable temporal sequence from exposure to the investigational agent, has been previously described in association with the investigational agent, and cannot reasonably be attributed to other factors such as the subject's clinical state, other therapeutic interventions or concomitant medications; AND the event disappears or improves with withdrawal of the investigational agent and/or re-appears on re-exposure (e.g., in the event of an infusion reaction).
- **Probable:** The event follows a reasonable temporal sequence from exposure to the investigational agent and has been previously been described in association with the investigational agent OR cannot reasonably be attributed to other factors such as the subject's clinical state, other therapeutic interventions or concomitant medications.
- **Possible:** The event follows a reasonable temporal sequence from exposure to the investigational agent, but could be attributable to other factors such as the subject's clinical state, other therapeutic interventions or concomitant medications.
- **Unlikely:** Toxicity is doubtfully related to the investigational agent(s). The event may be attributable to other factors such as the subject's clinical state, other therapeutic interventions or concomitant medications.
- **Unrelated:** The event is clearly related to other factors such as the subject's clinical state, other therapeutic interventions or concomitant medications.

For general AE assessment, an AE is considered related if it is assessed as definitely or probably related; unrelated if it is assessed as possibly, unlikely related or unrelated.

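### Sections 4.1.2 and 16.2 define a Phase I dose-limiting toxicity differently and neither takes precedence, so the same six subjects can lead to opposite trabectedin dose decisions

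*Combined protocol and SAP*

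**What the plan says.** Section 4.1.2 is headed as the DLT definition and applies to the Phase I portion. It counts "any grade 3 or higher adverse events, at least possibly-related to protocol therapy, which occur during the first 6 weeks of treatment". It then adds specifications. Laboratory abnormalities without clinical consequences that "resolve to grade 1 or better within 7 days will not be considered a DLT" are exempt. Named thresholds count, among them "Any elevation in AST and ALT over 8x institutional ULN will be considered a DLT" and "Any elevation in total bilirubin > 2x institutional ULN will be considered a DLT", together with cytopenias lasting 5 days or more. Expectedness is not a criterion.

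Section 16.2, Phase I Design, states: "Dose-limiting toxicities will be defined as unexpected, probably-related toxicities of grade 3 or higher". It has no laboratory thresholds and no exemption for transient abnormalities, and its first dose rule counts events over the whole of Phase 1 rather than in a 6-week window.

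Both sections feed the same decision. Two or more in the first six means a new cohort of six at 1.0 mg/m². Otherwise 1.5 mg/m² goes forward, because 4.1.2 and 16.1 choose the highest dose with fewer than two.

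Other sections bear on the difference:
- Section 9.6 separates possible from probable attribution and, for general adverse event assessment, treats an event as "unrelated if it is assessed as possibly, unlikely related or unrelated".
- Section 4.1.2 says "Expected toxicities are those outlined in" Section 10. Section 10.3 lists neutropenia, transaminase elevation and bilirubin elevation among the expected toxicities of trabectedin.
- Section 9.3 allows an event to be unexpected because of its severity or frequency as well as its nature.
- The trial-wide DSMB trigger is more than 30% of subjects with a DLT in 16.1 and 16.4, but 30% in 16.2.

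**The concern.** The DLT count is the only quantity in the Phase I dose rule. If two texts define it differently, the rule has no single answer, and whoever does the counting chooses the dose by choosing the section.

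The result affects more than the starting dose. Under 16.3, only Phase I subjects treated at the dose used in the expansion join the efficacy analysis, so the decision changes which six subjects are pooled with the 16 in Phase 2. It can also move total enrollment from 22 (6 + 16) to 34 (6 + 6 + 6 + 16). The DSMB's own trigger in 16.4, two of the first six with a DLT, depends on the same unsettled count.

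**Working it through.** The plan gives no operating characteristics for the DLT rule, so there is no stated figure to reproduce. The check is a comparison of the texts, followed by an illustration on assumed rates.

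**1. The two definitions side by side**

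| Element | Section 4.1.2 | Section 16.2 |
|---|---|---|
| Grade | 3 or higher, plus named laboratory thresholds | 3 or higher |
| Attribution | At least possible | Probable |
| Expectedness | Not considered | Must be unexpected |
| Transient laboratory abnormality | Exempt if no consequences and resolved within 7 days | No exemption |
| Time window | First 6 weeks | Whole of Phase 1 |

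Neither section refers to the other's definition, and no other section ranks them.

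**2. A case that the text alone decides**

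Two of the first six subjects each have a non-laboratory grade 3 event in weeks 1 to 6, rated possibly related.
- Under 4.1.2 the count is 2, so trabectedin is reduced to 1.0 mg/m².
- Under 16.2 the count is 0, because possible is below probable. Phase 2 proceeds at 1.5 mg/m².

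No judgement about expectedness is needed.

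**3. A case that depends on judgement**

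Two subjects have probably-related AST and ALT above 8x ULN that have not resolved within 7 days. Section 4.1.2 counts 2. Section 16.2 counts 0 if the events are taken as expected from the 10.3 list, and 2 if their severity or frequency is judged unexpected under 9.3. The 10.3 list gives no grades, and the note closing the immune-related tables in Section 10 says grade 3 hepatic toxicity happens only occasionally with trabectedin. Either reading can be defended.

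**4. The conflict can run the other way**

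An unexpected, probably-related grade 3 event arising after week 6 but during Phase 1 counts under 16.2 and not under 4.1.2. So 16.2 is usually the narrower definition, but it is not strictly contained in 4.1.2.

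**5. Illustration of size, on assumed rates**

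Let u be the chance that a subject has an event counted by both definitions, and e the chance that a subject without one has an event counted by 4.1.2 only. Ignore the reverse case in step 4. The rate under 4.1.2 is a = u + (1 − u)e. For six subjects with rate p, the chance of two or more is

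P(p) = 1 − (1 − p)^6 − 6p(1 − p)^5.

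In this model every event counted by 16.2 is also counted by 4.1.2, so the chance that 4.1.2 says reduce while 16.2 says proceed is P(a) − P(u). With u = 0.05, P(u) = 0.033. Differences are taken before rounding.

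| e | a | P(a) | P(a) − P(u) |
|---|---|---|---|
| 0.05 | 0.0975 | 0.109 | 0.077 |
| 0.10 | 0.145 | 0.212 | 0.179 |
| 0.20 | 0.24 | 0.442 | 0.409 |
| 0.40 | 0.43 | 0.810 | 0.778 |

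With u between 0.02 and 0.10, the result is 5% to 10% at e = 0.05 and 73% to 78% at e = 0.40.

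**6. The 30% wording**

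A threshold of 30% and one of more than 30% differ only where 0.30n is a whole number. Up to n = 34 that is n = 10 (3 versus 4 subjects), 20 (6 versus 7) and 30 (9 versus 10). The event definition matters more than this wording.

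**The case against.** The strongest reply is that 4.1.2 plainly governs: it is headed as the definition and is much more detailed. That is the better reading, but the statistical section says otherwise in a full sentence of its own. One might instead take the 16.2 sentence as meant for Phase 2, since the Phase 2 hold in 4.1.2 also uses unexpected and probably-related events. It stands under Phase I Design, however, and precedes the Phase I rule.

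A second reply is that safeguards exist. Clinically significant grade 3 or higher toxicities go to the DSMB, which must consider "whether there are increased frequency of known toxicities", and 10.4 requires individual dose reductions for listed events whatever their DLT status. These reduce the risk to subjects. They do not say which events enter the count.

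A third reply is that choosing 4.1.2 is a clinical decision, because 1.5 mg/m² is the US standard starting dose (2.6) and subjects must be clinically indicated for trabectedin (5.1). This stands, and is why the sponsor should confirm the choice with the DSMB.

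Several stronger readings are tempting but not supported:
- **Known trabectedin toxicity never counts under 16.2.** Section 9.3 leaves room for unusual severity or frequency.
- **Section 9.6 excludes possibly-related events from DLTs.** Its convention is for general adverse event assessment, and 4.1.2 sets its own attribution threshold. It shows only that possible and probable are different categories in this protocol.
- **The single-case rhabdomyolysis exemption in 10.3 proves that 4.1.2 governs.** Rhabdomyolysis is not on the bulleted expected list, so the exemption could be needed under either definition.
- **The transaminase rates in 2.6 are DLT rates.** The 38% is per cycle and described as reversible. The figure of about half of subjects comes from another trial and is not limited to 6 weeks. Neither applies the 4.1.2 criteria.
- **Phase 2 may open before the DLT window closes.** Section 4.1.2 speaks of completing the DLT period and allows replacement of non-completers, so the second-dose condition reads naturally as an additional minimum. It merits a clarifying phrase at most.

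**Conclusion.** The concern holds. Two current Phase I definitions of the same decision variable differ on attribution, expectedness, transient laboratory findings and time window, and no text says which prevails. This is an internal contradiction in a decision rule. The possibly-related example establishes it from the wording alone: 1.0 mg/m² under one section and 1.5 mg/m² under the other.

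The split for known trabectedin toxicities is conditional on how expectedness is judged. The range from 8% to 78% at u = 5% illustrates the arithmetic on assumed rates, with independent subjects and 16.2 events nested in 4.1.2 events. A reader should not take it as an estimate for this trial, because the documents give no DLT rate for the combination. The inconsistent 30% wording is real but minor.

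**What to change.** 1. Replace the defining sentence in 16.2 with: DLTs are defined in Section 4.1.2. That section is headed as the definition, gives the detail and, by counting possibly-related and expected events, is on the whole more protective.
2. State that the 6-week window of 4.1.2 applies to the 2-of-6 rule in 16.2.
3. Have the sponsor confirm the choice with the DSMB.
4. Use one threshold for the trial-wide trigger, more than 30% as in 16.1 and 16.4. State which DLT definition and time window it uses in Phase 2, since 4.1.2 defines DLTs only for Phase I. The separate Phase 2 hold in 4.1.2 concerns unresolved serious events and can remain as a second trigger.
5. As a minor clarification, say that each Phase I subject completes the 6-week window, has a DLT or is replaced before the dose decision and before Phase 2 opens.

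The edits are short, but the choice has a clinical cost: more frequent de-escalation from 1.5 mg/m² for known trabectedin toxicity than under 16.2. In the illustration with u = 0.05 and e = 0.20, de-escalation has probability 44% under 4.1.2 and 3% under 16.2. Waiting for the full window could delay Phase 2 by up to about 3 weeks, because the second trabectedin dose falls at Week 4, after about 3 of the 6 weeks.
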